1.2 Study Design

Study BT200-01 is a prospective, double-blind, randomized, placebo-controlled First-In-Human (FIH) study of BT200 in male and female NHVs with 4 sub-parts: Part A, a single ascending dose (SAD) study; Part B, a multiple ascending dose (MAD) study; Part C, a desmopressin challenge study; and Part D, a relative Bioavailability (BA) study.

Part A, the SAD study in NHVs, will be conducted according to an ascending dose cohort paradigm in which a unique cohort of NHVs will be treated at each single dose level. There will be 10 cohorts of NHVs (6:2 ratio of BT200:placebo; except for the sentinel pair [1:1 ratio]). Cohorts 1 through 10 will consist of 8 NHVs each, comprising 6 NHVs administered BT200 subcutaneous (SC) (0.18, 0.6, 1.8, 6.0, 12.0, 18.0, 24.0 by rapid SC injection, and 24.0, 36.0 mg, 48.0 mg by gradual SC infusion, respectively, for each cohort) and 2 NHVs administered placebo SC. Not all NHVs in a given cohort in Part A will be dosed on the same day: a sentinel pair (1 BT200, 1 placebo) will be dosed on the first day, then with a lag of at least 48 hours staggered groups roughly of 2 to 3 NHVs per day will be dosed thereafter. Cohorts 8-10 of Part A will be initiated only after submission and authorization of a Substantial Amendment to Ethics Committee (EC) and Austrian Agency for Health and Food Safety (AGES) summarizing the results of Cohorts 1-7.

Part B, the MAD study in NHVs, will also be conducted according to an ascending dose cohort paradigm. Part B will be initiated only after Substantial Amendment to EC and AGES has been submitted and authorized following completion of cohorts 8-10 of Part A and Part D. There will be 2 cohorts of NHVs, each consisting of 8 NHVs (6:2

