ratio of BT200:placebo) in this part of the study. These cohorts will be administered an initial loading dose regimen of BT200 or placebo consisting of both a 2-hour IV infusion and an SC injection on Day 0, followed by 4 weekly (every 7 days) doses of BT200 or placebo by SC injection. The dose levels in Part B are: a loading dose of 12.0 mg IV infused over 2 hours plus 12.0 mg SC injection followed by 4 maintenance doses of 12.0 mg SC injection in Cohort 13; a loading dose of 24.0 mg IV infused over 2 hours plus 24.0 mg SC injection followed by 4 maintenance doses of 24.0 mg SC injection in Cohort 14. Not all subjects in each of the cohorts of Part B will be dosed on the same day; rather, they will be dosed in staggered groups roughly of 2 to 3 subjects per day.

Part C, the desmopressin challenge will be initiated only after a Substantial Amendment to EC and AGES has been submitted and authorized following cohorts 8-10 of Part A and Part D. Part C will consist of a single cohort, Cohort 12, of 8 NHVs (6:2 ratio of BT200:placebo, plus desmopressin challenge) in this part of the study. Six subjects in Cohort 12 will be administered a single dose of 48.0 mg BT200 SC injection and 2 subjects administered a single dose of placebo on Day -4 as an SC injection. All subjects will then be administered an intravenous (IV) infusion of 0.3 μ g/kg desmopressin over 30 minutes on Day 0 approximately 96 hours after the single dose of BT200 or placebo SC (i.e., at the predicted time to maximum plasma concentration [T_{max}] for BT200).

Part D, the relative BA crossover, will be initiated only after a Substantial Amendment to EC and AGES has been submitted and authorized following cohorts 1-7 of Part A. Part D will consist of 1 cohort of NHVs, consisting of 8 NHVs (6:2 ratio of BT200:placebo) administered a single IV dose of BT200 of 24.0 and 2 NHVs administered a single dose of placebo IV over 24 hours on Day 0. Part D could include NHVs who have previously participated in Part A.

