Abbreviations: '=minute; BP=blood pressure; D=day; ECG=electrocardiogram; h=hour; HR=heart rate; Immuno=immunogenicity; MAD=multiple ascending dose; PD=pharmacodynamic(s); PK=pharmacokinetic(s); V=visit

1. Full physical examination only on Days 28 and 56.

2. Dipstick urinalysis will be performed.

3. Late PK samples will be obtained at 6 and 8 weeks after the last dose of study drug, whereas late immunogenicity samples will be obtained only at 8 weeks after the dose of study drug.

4. PD assessments also include biomarker assays and an exploratory coagulation assay.

Note: Additional details regarding Part B laboratory blood sampling (hematology, coagulation, clinical chemistry, PK assessments, immunogenicity assessments, and PD assessments [including biomarker assays and an exploratory coagulation assay]) are provided in CSP Appendix 2: Laboratory Blood Sampling Supplement to Schedule of Assessments (Part B) and the laboratory manual.

Table 4: Study Procedures Part C Weeks 1-9 (Desmopressin Challenge)

Visit	Scr	V1	V2										V3	V4	V5	V6	V7	V8	V9	PK and Immuno SaV
Day		Treatment										Post-treatment								
		D -4	D0									D1	D2	D3	D4	D7	D14	D21	D28	D42, D56
Time		-96h	-1h	0h	0.5h	1h	2h	3h	4h	8h	14h	24h	48h	72h	96h	168h				
Time Window	D-28 to D-5	±1h	±59'		±15'	±15'	±15'	±15'	±30'	±30'	±120'	±30'	±2h	±2h	±2h	±2h	±1d	±1d	±2d	
Written Informed Consent	X																			
Demographic Data	X																			
Medical History	X																			
Admit to Inpatient Unit			X																	
Inclusion / Exclusion Criteria	X		X																	
Randomization		X																		
Study Drug Administration		X																		
Desmopressin Administration				X																
Body Weight and Height ¹	X		X															X		
Physical Examination, Full	X															X			X	
Physical Examination, Brief			X										X				X	X		
Vital Signs (BP, HR, body temperature)	X		X		X	X	X	X	X	X	X	X	X	X	X	X	X	X		
Cardiac Evaluation (12-lead ECG)	X		X									X				X			X	
Serology for HIV, hepatitis B, and hepatitis C	X																			
Nasal swab screen for coronavirus	X																			

Adapted from:

STAT03_A Statistical Analysis Plan

Version 6.0, Effective Date 16-Feb-2018

Confidential and intellectual property of Assign DMB. No part of this document or its contents may be duplicated, referenced, published or otherwise disclosed in any form or by any means without prior written consent of Assign DMB.

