2.6 Descriptive Analyses

Descriptive analyses of continuous variables (summary statistics) will be described with the number of non-missing observations, arithmetic mean, standard deviation (\pm SD), median, quartiles (Q1 and Q3) and range (minimum and maximum).

Categorical variables (frequency statistics) will be described with the number of non-missing observations and percentages (%). Percentages will be calculated on the total number of non-missing observations, if not stated otherwise.

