5.2 Pharmacodynamics

The following tables will be performed for PFA-100, VWF:RiCo [%], multiplate aggregometer and REAADS and corresponding details on the subject level will be provided in data listings:

- Absolute values by time point
- Absolute change from randomization by time point
- Relative change [%] from randomization by time point

The following figures will be provided for PFA-100, VWF:RiCo [%], multiplate aggregometer and REAADS separately:

- Absolute values by subject: For every subject separately, the time course over of the parameters mentioned above will be drawn, where the actual measurement time point since first dose will be shown on x-axis (hours) and the parameters values will be drawn on the y-axis.
- Absolute values by cohort: One graph will be drawn that includes the data of all cohorts. One line will be drawn per cohort, where the x-axis will show the planned time point of measurement (in hours) and the y-axis will show the mean value of the respective cohort incl. standard error. Measurements of all scheduled visits will be included, where the EOS visit will be treated as the last visit.

PD sampling results will be entered eCRF using a result specifier (i.e. <, ≤, >, ≥). For statistical analysis, values reported as <x, ≤x, >x or ≥x will be analyzed as x. E.g. <300, ≤300, >300 or ≥300 will be analyzed as value 300.

Details are specified in Section [7](#).

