14.x.2.1.4	Yes	PFA-100 [sec]: Absolute values by time point (PP Population)	
14.x.2.1.5	No	PFA-100 [sec]: Absolute change from randomization by time point (PP Population)	
14.x.2.1.6	No	PFA-100 [sec]: Relative change [%] from randomization by time point (PP Population)	
14.x.2.1.7	Yes	REAADS: Absolute values by time point (PP Population)	
14.x.2.1.8	No	REAADS: Absolute change from randomization by time point (PP Population)	
14.x.2.1.9	No	REAADS: Relative change [%] from randomization by time point (PP Population)	
14.x.2.1.10	Yes	VWF:RiCo [%]: Absolute values by time point (PP Population)	
14.x.2.1.11	No	VWF:RiCo [%]: Absolute change from randomization by time point (PP Population)	
14.x.2.1.12	No	VWF:RiCo [%]: Relative change [%] from randomization by time point (PP Population)	
14.x.2.1.13	Yes	VWF antigen [%]: Absolute values by time point (PP Population)	
14.x.2.1.14	No	VWF antigen [%]: Absolute change from randomization by time point (PP Population)	
14.x.2.1.15	No	VWF antigen [%]: Relative change [%] from randomization by time point (PP Population)	
14.x.2.1.16	Yes	VWF propeptide [mIU/mL]: Absolute values by time point (PP Population)	
14.x.2.1.17	No	VWF propeptide [mIU/mL]: Absolute change from randomization by time point (PP Population)	
14.x.2.1.18	No	VWF propeptide [mIU/mL]: Relative change [%] from randomization by time point (PP Population)	
14.x.2.1.19	Yes	Factor VIIIc activity [%]: Absolute values by time point (PP Population)	
14.x.2.1.20	No	Factor VIIIc activity [%]: Absolute change from randomization by time point (PP Population)	
14.x.2.1.21	No	Factor VIIIc activity [%]: Relative change [%] from randomization by time point (PP Population)	
14.x.2.1.22	Yes	aPTT FS [sec]: Absolute values by time point (PP Population)	
14.x.2.1.23	No	aPTT FS [sec]: Absolute change from randomization by time point (PP Population)	
14.x.2.1.24	No	aPTT FS [sec]: Relative change from randomization by time point (PP Population)	
14.x.2.1.25	Yes	Thrombin generation CAT assay [nM]: Absolute values by time point (PP Population)	

14.x.2.1.26	No	Thrombin generation CAT assay [nM]: Absolute change from randomization by time point (PP Population)	
14.x.2.1.27	No	Thrombin generation CAT assay [nM]: Relative change [%] from randomization by time point (PP Population)	
14.x.2.1.28	Yes	Fibrin D-dimer [mIU/mL]: Absolute values by time point (PP Population)	
14.x.2.1.29	No	Fibrin D-dimer [mIU/mL]: Absolute change from randomization by time point (PP Population)	

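### Setting limit-censored PD results to the limit pulls cohort means toward it and shrinks the plotted standard error, and the cohort figures and change tables do not show where this happens

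*SAP*

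**What the plan says.** SAP 5.2 (Pharmacodynamics) records a result specifier in the eCRF and gives a substitution rule: "For statistical analysis, values reported as <x, ≤x, >x or ≥x will be analyzed as x". Its illustration is "E.g. <300, ≤300, >300 or ≥300 will be analyzed as value 300", with no assay or unit named. The rule covers lower and upper limits alike.

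The same section plans tables of absolute values, absolute change and relative change from randomization for the four PD assays. It also plans a figure by cohort in which "the y-axis will show the mean value of the respective cohort incl. standard error". Cohorts are small: in Part A each is described as "comprising 6 NHVs administered BT200 subcutaneous (SC" with two on placebo (SAP 1.2), and SAP 2.5 gives 6:2 for Parts B, C and D.

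SAP 2.6 adds to n, mean and SD the "median, quartiles (Q1 and Q3) and range (minimum and maximum"). It lists no count of values at a limit. The PD entries in SAP 7.1, for example "PFA-100 [sec]: Absolute change from randomization by time point (PP Population"), and the cohort figures in SAP 7.3 have empty comment columns. Among the PD outputs, only listing 16.2.x.2.1 in SAP 7.2 carries the specifier.

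**The concern.** A result of `>x` means that the true value is somewhere above x. Analysing it as x discards that. If several of six subjects are beyond the limit, their different true values become one number. The cohort mean stops moving with dose and the spread between subjects collapses. The error bar therefore narrows as more subjects pass the limit, which is when least is known about the true mean.

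The PD tables of absolute values and the cohort figures are flagged for the topline analysis, so they are an early picture of effect by dose. At stake is whether that picture separates a real plateau with little variation from an assay that has run out of range.

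**Working it through.** There is no figure in the plan to reproduce: SAP 1.4 gives no power or sample size calculation, and no PD standard deviation or assay limit is stated. The effect of the rule was therefore computed directly.

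**Inputs.** From the documents: six BT200 subjects per cohort, substitution of x, mean and SE plotted. Assumed: one common limit per assay and time point; normal or log-normal values; the share p beyond the limit varied.

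**Direction.** Replacing values by one common limit never increases the difference between any two subjects. The SD and SE of absolute values can only stay the same or shrink.

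**Normal data, upper limit.** With standard normal Z and limit c, where P(Z > c) = p:
- mean of min(Z, c) = −φ(c) + c·p
- variance v(p) = (1−p) − c·φ(c) + c²·p − mean²

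At p = 0.5, c = 0 and φ(0) = 0.399. The mean is −0.399 SD, v = 0.5 − 0.159 = 0.341, and the SD ratio is √0.341 = 0.58. The SE row below averages 400,000 simulated cohorts of six.

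**Log-normal data, log-SD s = 0.3 to 0.5, median 1.** The true mean is M = exp(s²/2) and the upper limit is x = exp(s·c). The analysed mean is M·Φ(c−s) + x·p. At s = 0.5, p = 0.5: M = 1.133, analysed mean 0.850, shortfall 0.283/1.133 = 25%. The lower-limit row uses the mirror formula.

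| Share capped | 10% | 25% | 50% |
|---|---|---|---|
| Shown/true SD, normal | 0.91 | 0.79 | 0.58 |
| Average shown/true SE of six, normal | 0.92 | 0.79 | 0.55 |
| Mean understated, upper limit, log-normal (% of true mean) | 2-5 | 6-12 | 14-25 |
| Mean overstated, lower limit, log-normal (% of true mean) | about 1 | 3-4 | 10-13 |
| Chance that 4 or more of 6 are capped | 0.1% | 4% | 34% |

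**Change from randomization.** With an uncapped baseline B, E[min(Y, x) − B] − E[Y − B] = E[min(Y, x)] − E[Y]. The mean change is off by the same absolute amount as the mean. The SD of change behaves differently: Var = s_B² + s_Y²·v(p) − 2ρ·s_B·s_Y·(1−p). With equal SDs and p = 0.5, shown/true SD is 0.86 at ρ = 0.3 and 1.16 at ρ = 0.8. With post-dose SD two to three times baseline it is 0.57 to 0.68. It may fall or rise.

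**Illustration (assumed values, limit 300).** True values 240, 320, 340, 380, 420, 520: mean 2220/6 = 370, SD 95.3, SE 95.3/√6 = 38.9, median 360. Under the rule they become 240 and five times 300: mean 1740/6 = 290, SD 24.5, SE 24.5/√6 = 10.0, median 300. If all six exceed 300, the SE is 0.

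**What the tables reveal.** Take an upper limit, six values, and quartiles at the 2nd and 5th ordered values:

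| Pattern in the absolute-value table | Number at x |
|---|---|
| Only the maximum is x | 1 |
| Q3 = maximum, median lower | 2 or 3 |
| Median = Q3 = maximum, Q1 lower | 4 |
| Q1 = x, minimum lower | 5 |
| Minimum = maximum | 6 |

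In the change tables each capped value has its own baseline subtracted, so these ties disappear. The cohort figures show only mean and SE.

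**The case against.** The best defence is that the plan already discloses much of this. The rule is stated openly. As the last table shows, the planned quantiles of six absolute values give the number at the limit to within about one, barring genuine results equal to x. The extreme case announces itself as SD 0 with minimum equal to maximum. Each subject's time course is plotted, where capping appears as a plateau, and both those plots and listing 16.2.x.2.1 are part of the topline output. This stands: it would be wrong to infer that a reader has no way to tell how many values are capped.

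It is also fair that nothing shows the problem to be large here. The documents identify no assay, dose or time point with a sizeable share beyond a limit. At 10% capped the effect on normal data is small. PD is exploratory and no inferential testing is planned (SAP 1.4).

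The defence does not reach the cohort figures or the change tables, and it does not correct the mean, SD and SE printed in the absolute-value tables. A reader who spots the pattern still has to work back to what the numbers mean.

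**Conclusion.** The point holds as a conditional one. Wherever values lie beyond a common limit, the rule moves the mean and mean change toward it and gives an SE of absolute values that is too small or, at best, unchanged. The effect is modest at about 10% capped and material from roughly 25-50%, where the plotted SE averages 0.79 to 0.55 of its true size for normal data. These sizes rest on the assumed distributions, a common limit and an uncapped baseline. If limits differ between samples, the SE result need not hold.

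Three stronger readings are not supported:
- That every SD is understated: the SD of change can go either way.
- That the example value of 300 belongs to a particular assay: the SAP does not say so.
- That dose choices or conclusions were distorted: no test or decision rule uses these summaries. The protocol synopsis assigns PK and PD analysis to a separate vendor, whose handling of limit values is not visible here.

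**What to change.** Amend SAP 5.2 and the PD entries in Section 7 as follows.

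1. In the value and change tables, show n (%) above the upper limit and below the lower limit, per cohort and time point.
2. For absolute values, rank `>x` highest and `<x` lowest when taking the planned median and quartiles. Print `>x` or `<x` when the quantile is itself censored.
3. Where any value is at a limit, footnote the mean as a lower bound (upper limit) or an upper bound (lower limit). Footnote the SD and SE of absolute values as understated, and the SD of change as unreliable in either direction. If both limits occur at one time point, say that neither bound applies to the mean.
4. Mark the affected points in the cohort figures.

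The cost is a little extra programming and busier tables. No new data are needed, because the eCRF holds the specifier. SAP 8 fixes no table shells and sends draft outputs on dummy allocation to the sponsor for review, so the additions can be made at that step.

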5.3 Biomarker

The following tables will be performed for VWF antigen [%], VWF propeptide [mIU/mL], Factor VIIIc activity [%], aPTT FS [sec], Thrombin generation CAT assay (Thrombinoscope) [nM], Fibrin D-dimer [mIU/mL] and Prothrombin fragment F1.2 [mIU/mL]. Corresponding details on the subject level will be provided in data listings:

- Absolute values by time point
- Absolute change from randomization by time point
- Relative change [%] from randomization by time point

The following figures will be provided for VWF antigen [%], VWF propeptide [mIU/mL], Factor VIIIc activity [%], aPTT FS [sec], Thrombin generation CAT assay (Thrombinoscope) [nM] and Fibrin D-dimer [mIU/mL] and Prothrombin fragment F1.2 [mIU/mL] separately:

- Absolute values by subject: For every subject separately, the time course over of the parameters mentioned above will be drawn, where the actual measurement time point will be shown on x-axis (hours) and the parameters values will be drawn on the y-axis.
- Absolute values by cohort: One graph will be drawn that includes the data of all cohorts. One line will be drawn per cohort, where the x-axis will show the planned time point of measurement (in hours) and the y-axis will show the mean value of the respective cohort incl. standard error. Measurements of all scheduled visits will be included, where the EOS visit will be treated as the last visit.

Details are specified in Section 7.

5.4 Immunogenicity

The following tables will be produced for immunogenicity and corresponding details on the subject level will be provided in data listings:

- ADA results (positive/negative/not reportable/NA) by time point

Details are specified in Section 7.

6. SAFETY ANALYSIS

All analyses will be performed for the Safety Population. Data from unscheduled visits will only be listed. Data from scheduled visits and early termination visits will be tabulated.

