6.3 Laboratory Parameters

Laboratory data from scheduled visits and early termination visits will be tabulated. Listings will additionally include results from unscheduled visits.

The following parameters will be assessed in the study and will be included in the statistical analysis:

- Hematology
 - Hemoglobin
 - Hematocrit
 - Red blood cells
 - White blood cells
 - Lymphocytes
 - Monocytes
 - Neutrophils
 - Eosinophils
 - Basophils
 - Platelets
 - Reticulocytes
- Coagulation
 - Prothrombin time
- Clinical Chemistry
 - Sodium
 - Potassium
 - Calcium
 - Chloride
 - Aspartate aminotransferase
 - Alanine aminotransferase
 - Alkaline phosphatase
 - Lactate dehydrogenase
 - Gamma-glutamyltransferase
 - Bilirubin
 - C-reactive protein
 - Blood Urea Nitrogen
 - Creatinine

- Glucose
- Urinalysis
 - Specific gravity
 - pH
 - Leukocytes
 - Nitrite
 - Protein
 - Glucose
 - Ketones
 - Urobilinogen
 - Bilirubin
 - Erythrocytes

Quantitative laboratory parameters (i.e., hematology, clinical chemistry, coagulation, pH, Specific Gravity) will be analyzed descriptively:

- Absolute values by parameter and time point (summary statistics)
- Absolute change from randomization by parameter and time point (summary statistics)
- Relative change from randomization by parameter and time point (summary statistics)
- Number of subjects with values above/below normal range by parameter and time point (frequency statistics)

Qualitative urinalysis parameters will be analyzed by tabulation of urinalysis result by parameter and time point (frequency statistics)

One set of data listings will show parameters outside normal range (hematology, coagulation, clinical chemistry, quantitative urinalysis parameters) and abnormal qualitative urinalysis values, respectively.

For every parameter, boxplots showing the absolute values by study day will be provided.

All parameters will be analyzed using the unit registered by study site in the eCRF. No unit conversion will be done.

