6.4 Other Safety Parameters

Other safety data from scheduled visits will be tabulated as described below. Listings will additionally include results from unscheduled visits or early termination visit.

Results from vital signs (systolic blood pressure [mmHg], diastolic blood pressure [mmHg], heart rate [beats/min], body temperature [C] and body weight [kg]) and ECG will be tabulated descriptively by:

- Absolute values by parameter and time points (summary statistics)
- Absolute changes from randomization by parameter and time points (summary statistics)
- Number of subjects with clinically relevant vital signs results by parameter and time point (frequency statistics)

- ECG Interpretation (normal/abnormal/abnormal, clinically relevant/abnormal, not clinically relevant) by time point (frequency statistics)
- Physical examination results (normal/abnormal) by body system and time point (frequency statistics)

Absolute values of vital signs parameters and continuous ECG parameters will be provided by time point. The x-axis will show the study day. A separate figure will be provided for every parameter.

Details are specified in Section [7](#).

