14.x.3.1.11	Yes	Related serious AEs and bleeding events by maximum severity (Safety Population)	Incl. 2-sided 95% CIs
14.x.3.1.12	Yes	AEs and bleeding events leading to permanently study drug discontinuation or leading to withdrawn from study by SOC and PT (Safety Population)	
14.x.3.1.13	Yes	Related AEs and bleeding events leading to permanently study drug discontinuation or leading to withdrawn from study by SOC and PT (Safety Population)	
14.x.3.1.14	Yes	Bleeding Events by SOC and PT (Safety population)	Incl. 2-sided 95% CI
14.x.3.1.15	Yes	Major bleeding events overall and by SOC and PT (Safety Population)	
14.x.3.1.16	Yes	Total ISTH Bleeding Score (Safety Population)	
14.x.3.1.17	Yes	Bleeding Assessment Score by Symptom (Safety Population)	
14.x.3.1.18	Yes	Maximum Bleeding Assessment Score (Safety Population)	
Laboratory parameter			
14.x.3.1.19	Yes	Hematology and Coagulation: Absolute values by time point (Safety Population)	
14.x.3.1.20	Yes	Hematology and Coagulation: Absolute change from randomization by time point (Safety Population)	
14.x.3.1.21	Yes	Hematology and Coagulation: Relative change from randomization by time point (Safety Population)	

14.x.3.1.22	Yes	Hematology and Coagulation: Subjects outside normal range by time point (Safety Population)	
14.x.3.1.23	Yes	Clinical Chemistry: Absolute values by time point (Safety Population)	
14.x.3.1.24	Yes	Clinical Chemistry: Absolute change from randomization by time point (Safety Population)	
14.x.3.1.25	Yes	Clinical Chemistry: Relative change from randomization by time point (Safety Population)	
14.x.3.1.26	Yes	Clinical Chemistry: Subjects outside normal range by time point (Safety Population)	
14.x.3.1.27	Yes	Quantitative Urinalysis: Absolute values by time point (Safety Population)	
14.x.3.1.28	Yes	Quantitative Urinalysis: Absolute change from randomization by time point (Safety Population)	
14.x.3.1.29	Yes	Quantitative Urinalysis: Relative change from randomization by time point (Safety Population)	
14.x.3.1.30	Yes	Quantitative Urinalysis: Subjects outside normal range by time point (Safety Population)	
14.x.3.1.31	Yes	Qualitative Urinalysis by time point (Safety Population)	
14.x.3.1.32	Yes	Vital Signs: Absolute values by time point (Safety Population)	
 • systolic blood pressure [mmHg] • diastolic blood pressure [mmHg] • heart rate [beats/min] • body temperature [C] • body weight [kg]

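### The laboratory, vital-sign and ECG abnormality tables count subjects visit by visit and omit unscheduled results, so no planned table of these measurements shows how many subjects were ever affected

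*SAP*

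**What the plan says.** SAP Section 6 sets the general rule. Unscheduled visits: "Data from unscheduled visits will only be listed". Other visits: "Data from scheduled visits and early termination visits will be tabulated".

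Section 6.3 repeats this for the laboratory: "Laboratory data from scheduled visits and early termination visits will be tabulated. Listings will additionally include results from unscheduled visits". Its abnormality summary is "Number of subjects with values above/below normal range by parameter and time point (frequency statistics").

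Section 6.4 covers vital signs, ECG and physical examination. It tabulates scheduled visits and adds: "Listings will additionally include results from unscheduled visits or early termination visit". Its abnormality summary for vital signs is "Number of subjects with clinically relevant vital signs results by parameter and time point (frequency statistics").

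Section 7.1 follows the same pattern. Table 14.x.3.1.22 is "Hematology and Coagulation: Subjects outside normal range by time point (Safety Population"), and Table 14.x.3.1.26 is "Clinical Chemistry: Subjects outside normal range by time point (Safety Population"). Tables .30 (quantitative urinalysis), .34 (clinically relevant vital signs), .37 (clinically relevant ECG) and .39 (physical examination) are also by time point.

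In Section 7.2, the listings of out-of-range haematology and coagulation values (16.2.x.3.17) and clinical chemistry (16.2.x.3.18) are part of the topline. The vital-sign and ECG listings (16.2.x.3.21 and .22) are not, nor are those for urinalysis (.19 and .20) and physical examination (.23).

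Section 1.3.1 includes clinically relevant laboratory, vital-sign, ECG and physical findings in the primary endpoint, where they may point to an organ affected by BT200.

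**The concern.** Two features combine. First, a result from an unscheduled visit cannot enter any of the abnormality tables, whatever it shows. Second, the tables never collapse over visits, so even for scheduled visits the reader cannot tell whether several subjects were affected once each or one subject repeatedly. Judging a pattern of toxicity depends on that distinction.

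With 6 BT200 subjects per cohort, each subject is about 17 percentage points. A set of tables showing no affected subject, when there was one, could mislead anyone who reads the tables without working through the listings. This applies most to the Part A and D topline, where the vital-sign and ECG listings are not produced.

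**Working it through.** The plan gives no figure to reproduce. SAP Section 1.4 describes the study as descriptive, and the documents give neither observed counts nor a rate of unscheduled visits. The check is therefore a reading of the SAP plus an illustration with assumed counts.

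**Step 1. Is there a subject-level row anywhere?** Sections 6, 6.3, 6.4 and 7.1 to 7.3 were read for any table, row or figure giving an any-time or worst post-dose result for laboratory values, vital signs, ECG or physical examination. There is none. The figures are also by visit, study day or time point.

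**Step 2. Finding at an unscheduled visit only.** Input: 6 BT200 subjects per cohort (SAP Section 1.2). Assumed: one subject has a clinically relevant value, at an unscheduled visit only.
- Planned tables: 0/6 = 0% at every time point.
- Ever affected: 1/6 = 16.7%.
- Difference: 16.7 percentage points.

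**Step 3. Findings at several scheduled visits.** Let n_t be the count at scheduled visit t. From these counts alone, the number ever affected lies between max(n_t) and min(6, sum of n_t). Assumed: n_t = 1 at each of three visits.
- Lower bound: max(1, 1, 1) = 1, so 1/6 = 16.7%.
- Upper bound: min(6, 1 + 1 + 1) = 3, so 3/6 = 50.0%.

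The tables are identical in both cases.

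**Step 4. What do the laboratory tables count?** Tables .22, .26 and .30 count values outside the normal range. The investigator's clinical-relevance flag for laboratory values appears only in the listings (16.2.x.3.17 to .20). The endpoint speaks of clinically relevant abnormalities, so even at a scheduled visit these are not counted as such in a laboratory table.

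**Step 5. Would a plain ever-out-of-range row do?** Assume a 5% chance per test of falling outside the range in an unaffected subject, independent tests, and 5 to 8 post-dose samples. The share of unaffected subjects flagged at least once per parameter is 1 − 0.95^k:
- k = 5: 1 − 0.774 = 22.6%.
- k = 8: 1 − 0.663 = 33.7%.

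Subjects already out of range before dosing would be added to these. The row therefore needs the clinical-relevance flag or a pre-dose condition.

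**Step 6. Early termination visits.** Section 6 says they are tabulated, and Section 6.3 agrees for the laboratory. Section 6.4 sends them to listings only. The two rules conflict for vital signs, ECG and physical examination.

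**The case against.** The strongest reply is that nothing is lost. Unscheduled results are listed by subject with a clinical-relevance flag, and in cohorts of this size a reader can count affected subjects by hand and separate three subjects once from one subject three times. The haematology, coagulation and chemistry listings are in the topline, and all the listings are in the final analysis. This stands. A reader might infer that such a finding goes unreported altogether, and the documents do not support that. What is missing is the summary count.

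A second reply is that the finding may be recorded as an adverse event. The adverse-event tables are not by time point and are in the topline. This stands in part. The supplied text contains no rule requiring that entry, but the protocol's adverse-event reporting section is not in the supplied text, so one cannot say the route is closed. The supportable statement is that the finding is in none of the laboratory, vital-sign or ECG abnormality tables, not that it is in no table at all.

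Third, the endpoint is worded as patterns, not as an incidence, and the study is descriptive. A reader might infer that the plan contradicts its own endpoint. It does not, because no subject-level percentage was promised. The request is itself only a descriptive count.

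Two further inferences should be resisted. The plan would not print a confidence interval around 0/6: intervals are marked only for the adverse-event and bleeding tables 14.x.3.1.1, .8 to .11 and .14. And the documents do not say why, or how often, unscheduled visits occur, so the share of important findings that falls there is unknown.

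Keeping unscheduled values out of by-visit means is sound practice, and nothing here argues against it.

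**Conclusion.** The point holds as a gap in summary reporting that should be closed. By stated rule, a clinically relevant finding seen only at an unscheduled visit is in none of the laboratory, vital-sign or ECG abnormality tables, and no planned table of these measurements gives the number of subjects ever affected. For a component of the primary endpoint, the tables can show 0/6 where the answer is 1/6, or leave anything from 1/6 to 3/6 open. These sizes rest on 6 BT200 subjects per cohort and on assumed counts; they are not a prediction.

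The gap is widest in the Part A and D topline. There, an unscheduled vital-sign or ECG finding appears only if it was also recorded as an adverse event. In the final report it is a matter of having to count from listings.

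**What to change.** - Keep the existing by-visit rows on scheduled visits.
- For each parameter in Tables 14.x.3.1.22, .26, .30, .34 and .37, add one row counting each Safety Population subject once if any post-dose record (scheduled, unscheduled or early termination) is clinically relevant and the pre-dose record was not. Name the pre-dose record to be used in each part.
- For laboratory values, use the clinical-relevance flag already planned for the listings. If out-of-range values are also counted over all visits, restrict them to subjects in range before dosing.
- Add a similar row to Table .39 for new abnormal physical examination findings.
- Use subjects with at least one post-dose value as the denominator. A confidence interval is optional; if one is given, name the method.
- Mark the new rows for the topline.
- Reconcile Sections 6 and 6.4 on whether early termination visits are tabulated.

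The cost is SAP wording and a little extra programming, with no new data. One drawback remains: an ever-affected count rises with the number of assessments, so it should be read against the placebo column. In Part A that column pools 10 cohorts × 2 = 20 planned subjects; in Parts C and D it holds only 2, so the comparison there will be weak.
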